5.2. Number of Participants

Up to 8 subjects may be enrolled. It is planned that up to 6 subjects will be dosed initially and 2 additional subjects may be dosed if needed, in order that a minimum of 4 subjects complete the study. For purposes of this study, a subject completes the study when all scheduled procedures shown in the Schedule of Activities (Section 2) have been finished.

5.3. End of Study Definition

End of the study is the date of the last visit or last scheduled procedure shown in the Schedule of Activities (Section 2) for the last subject.

5.4. Scientific Rationale for Study Design

This clinical study will be conducted to determine the disposition of radioactivity and PK of tirzepatide in healthy male subjects following a single SC injection of tirzepatide labeled with ^{14}C . The radiolabeled tirzepatide enables identification of circulatory and excretory metabolites and understanding of the clearance pathways.

Conducting the study in healthy subjects mitigates the potential confounding effects of the disease state and of concomitant medications. This study has an open-label design with no control treatment. This type of design is standard and widely used in radiolabeled studies. Subcutaneous administration has been chosen as this is the intended clinical route of tirzepatide administration.

Based on available clinical PK data for tirzepatide and human excretion data from a related GLP-1 analog (Jensen et al., 2017), the duration of clinical confinement will be up to 14 days postdose (Day 15).

5.5. Justification for Dose

Based on data from a quantitative whole-body autoradiography disposition study for tirzepatide in male rats, a whole-body radiation dose in a 70-kg man following administration of a single SC 100- μCi (3.7-MBq) dose of [^{14}C]-tirzepatide was calculated to be 97.7 mrem (0.977 mSv). This effective radiation dose is defined as being within dose limits for members of the public (Category II study; World Health Organization, 1977) with a minor associated risk (risk Category IIa; International Commission on Radiological Protection [ICRP], 1992). Therefore, administration of a single SC 100- μCi (3.7-MBq) dose of [^{14}C]-tirzepatide would not be expected to represent a significant radiation exposure risk in man.

The specific activity of [^{14}C]-tirzepatide is approximately 20-24 $\mu\text{Ci}/\text{mg}$. A dose of tirzepatide that can provide a radioactive dose of 100 μCi per subject, is considered sufficient to facilitate characterization of the physiological disposition and metabolism of tirzepatide whilst complying with the “as low as (is) reasonably achievable” (ALARA) principle prescribed by the ICRP. Hence a tirzepatide dose of approximately 4.1 mg has been selected for this study.

Data from Phase 1 study GPGA has shown that a 5-mg dose of tirzepatide was well tolerated by healthy subjects and patients with T2DM, and is also planned as one of the doses to be

investigated in Phase 3 studies. Doses higher than 5 mg were achieved via escalation since a 5 mg dose was considered the MTD when administered as a single dose.

The study will be submitted for approval by the Administration of Radioactive Substances Advisory Committee.

6. Study Population

Eligibility of subjects for the study will be based on the results of screening medical history, physical examination, vital signs, clinical laboratory tests, and ECGs.

The nature of any conditions present at the time of the physical examination and any preexisting conditions will be documented.

Screening may occur up to 27 days prior to check-in. Subjects who are not enrolled within 27 days of screening may be subjected to an additional medical assessment and/or clinical measurements to confirm their eligibility.

Prospective approval of protocol deviations to recruitment and enrollment criteria, also known as protocol waivers or exemptions, are not permitted.

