3.1. Study Rationale

Tirzepatide is being developed for the treatment of type 2 diabetes mellitus (T2DM) as an adjunct to diet and exercise. In addition, it is being developed as a therapy for the indications of chronic weight management and nonalcoholic steatohepatitis.

Study I8F-MC-GPHX (GPHX) is being conducted to determine the disposition of radioactivity and pharmacokinetics (PK) of tirzepatide (LY3298176) in healthy male subjects following a single subcutaneous (SC) injection of approximately 4.1 mg tirzepatide containing approximately 100 μ Ci [14 C]-tirzepatide. The 100- μ Ci dose of the radiotracer will be administered to each subject to facilitate characterization of physiological disposition and metabolism of tirzepatide. The tirzepatide dose is therefore dependent upon the specific activity of the drug substance. At the target drug substance specific activity, the tirzepatide dose will be 4.1 mg. However, based on variability in the drug substance specific activity, the final tirzepatide dose will be approximately 4.1 mg and will be no higher than 5 mg.

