9.3. Treatment of Overdose

For the purposes of this study, an overdose of tirzepatide is considered any dose higher than the planned study dose.

There is no specific antidote for tirzepatide. In the event of an overdose, the subject should receive appropriate supportive care and any AEs should be documented.

Refer to the IB.

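### Does the 4.1 mg dose contradict the protocol's own specific activity, and could a permitted dose count as an overdose?

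*Protocol*

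**What the plan says.** Protocol Section 5.5 (Justification for Dose) states that the specific activity of the labelled drug "is approximately 20-24" µCi/mg. It takes 100 µCi per subject as sufficient to characterise disposition and ends with "Hence a tirzepatide dose of approximately 4.1 mg has been selected for this study".

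Section 3.1 (Study Rationale) explains how mass and radioactivity are linked: "The tirzepatide dose is therefore dependent upon the specific activity of the drug substance". It continues: "At the target drug substance specific activity, the tirzepatide dose will be 4.1 mg". Allowing for variability in specific activity, it adds that "the final tirzepatide dose will be approximately 4.1 mg and will be no higher than 5 mg". The target specific activity is not given as a number. Section 3.3 assesses benefit and risk at a single maximum of 5 mg.

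The objectives in Section 4 and the treatment table in Section 7.1 (Table GPHX.2) carry only the approximate figures of 4.1 mg and 100 µCi.

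Section 9.3 (Treatment of Overdose) says that "an overdose of tirzepatide is considered any dose higher than the planned study dose". It gives no figure in mg and no tolerance.

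**The concern.** Section 5.5 presents 4.1 mg as following from the two numbers before it, yet every specific activity inside the printed range gives a larger mass. The low end of the range gives 5 mg, which is both the Section 3.1 ceiling and the dose that Sections 3.2 and 5.5 call the single-dose maximum tolerated dose. A reader of Section 5.5 alone would suspect that either the mass or the radioactivity is misquoted.

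The overdose definition adds to this. If the planned dose means 4.1 mg, a dose of 4.2 to 5.0 mg prepared within the Section 3.1 allowance is an overdose by the letter of Section 9.3. At stake would be wrongly classified subjects in a study of at most 8, and doubt about the denominator of the primary endpoint, which is a percentage of the radioactive dose.

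**Working it through.** **Inputs.** Specific activity about 20 to 24 µCi/mg (Section 5.5); radioactive dose 100 µCi (Sections 3.1 and 5.5, elsewhere called approximate); mass dose about 4.1 mg (Sections 3.1, 4, 5.5 and 7.1); ceiling 5 mg (Section 3.1).

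**Formula.** Mass (mg) = radioactivity (µCi) / specific activity (µCi/mg).

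**1. The protocol's own figure.** Section 3.1 ties 4.1 mg to an unstated target. Solving for it gives 100/4.1 = 24.39 µCi/mg, which is 24.39/24 − 1 = 1.6% above the printed upper limit and rounds to 24.

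**2. Mass needed for 100 µCi.**

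| Specific activity (µCi/mg) | Mass (mg) | Relative to 4.1 mg |
|---|---|---|
| 24 | 100/24 = 4.17 | +1.6% |
| 22 | 100/22 = 4.55 | +10.9% |
| 20 | 100/20 = 5.00 | +22.0% |

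**3. Radioactivity in exactly 4.1 mg.** 4.1 × 24 = 98.4 µCi; 4.1 × 20 = 82.0 µCi. At the top of the range, the approximate mass and the approximate radioactivity hold together.

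**4. Effect of rounding.** Suppose, as an assumption, that 20 and 24 are rounded to whole numbers. The range is then 19.5 to 24.5 µCi/mg, and the upper end gives 100/24.5 = 4.08 mg, so 4.1 mg is covered. At the lower end, 100/19.5 = 5.13 mg would pass the ceiling; 5 mg would then carry 5 × 19.5 = 97.5 µCi, still close to 100.

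**5. The ceiling.** 100/20 = 5.00 mg. The lowest printed specific activity gives exactly the Section 3.1 maximum, which is also the dose used in Section 3.3. These passages agree.

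**6. What the results depend on.**
- *Mass balance.* The recovery release criterion (Protocol Section 5.1, SAP Section 5) uses the actual dose, and Section 7.1 keeps each syringe for measurement of residual radioactivity.
- *Pharmacokinetics.* AUC and Cmax are not divided by dose. CL/F and V/F are: using 4.1 mg when 5.0 mg was given would scale them by 4.1/5.0 = 0.82. SAP Section 6 has the tables show the dosage actually administered, so the correct figure is at hand.
- *Safety.* Section 9.3 attaches supportive care and recording of adverse events to an overdose. Section 9.2 already requires adverse events to be recorded for every subject, and SAP Section 9.4.1 lists them all. The SAP has no table, exclusion or population rule that depends on overdose status.

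**The case for a change.** The best case for acting rests on Section 9.3. The treatment table, the objectives and the dose justification all show about 4.1 mg, so a reader can fairly take that as the planned dose. Sections 3.1 and 3.3 support 5 mg equally well. The same subject could be classed either way, and the SAP's treatment label, which leaves the dose to be filled in, shows that variation is expected. In addition, describing a dose as about 4.1 mg fits poorly when it may be 22% higher, and the one number that would settle the matter, the target specific activity, is missing.

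These three points stand as remarks on the wording. They do not amount to an arithmetic error. The figure of 4.1 mg was never offered as the middle of the range; Section 3.1 places it at the target. The overdose conflict appears on only one of two readings, and on neither does the classification feed an analysis. The one indirect route is SAP Section 8, where protocol deviations are weighed when subjects are assigned to populations. It would matter only if a dose that Section 3.1 allows were treated as a deviation severe enough to remove a subject.

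Two stronger claims do not stand. Mass and radioactivity can both be as stated, since 24 µCi/mg gives 98.4 µCi in 4.1 mg. Nor do the documents show that late radioactivity would be harder to detect, because they give no counting limit.

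**Conclusion.** The concern does not call for a change. The division is right (4.17 to 5.00 mg), but the gap between 4.1 mg and the nearest end of the range is 1.6%, within what approximate figures allow, and the 5 mg ceiling matches the other end exactly. What is left is missing detail: an unstated target specific activity, an approximate dose that may be exceeded by up to 22%, and an undefined reference dose in Section 9.3. Filling these in would make the protocol clearer without altering the mass balance, pharmacokinetic or safety results.

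This rests on three assumptions: that percentages of dose use the radioactivity actually given, that CL/F and V/F use the mass actually given, and that no subject is excluded for a dose within the Section 3.1 allowance. The first follows the stated release criterion, the second is in line with SAP Section 6, and nothing in the SAP calls for such an exclusion. Dose preparation is detailed in a Pharmacy Protocol that is not among the documents.

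On one reading, Sections 3.1 and 9.3 disagree over a dose between 4.1 and 5 mg. Which reading is meant is for the sponsor to reconcile; this note takes no view on the right dose or overdose rule.

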6.1. Inclusion Criteria

Subjects are eligible for inclusion in the study only if they meet all of the following criteria at screening and/or check-in:

- [1] are overtly healthy males, as determined by medical history and physical examination
 - [1a] male subjects, regardless of their fertility status, with non-pregnant women of childbearing potential partners must agree to either remain abstinent (if this is their preferred and usual lifestyle) or use condoms plus 1 additional highly effective (less than 1% failure rate) method of contraception (such as combination oral contraceptives, implanted contraceptives, or intrauterine device) or effective method of contraception, (such as diaphragms with spermicide or cervical sponge) for the duration of the study and for at least 90 days following administration of the investigational product (IP). A full list of permitted highly effective and effective methods of contraception is presented in [Appendix 7](#).
 - [1b] male subjects and their partners may choose to use a double-barrier method of contraception. Barrier protection methods without concomitant use of a spermicide are not an effective or acceptable method of contraception. Thus, each barrier method must include use of a spermicide. It should be noted, however, that the use of male and female condoms as a double-barrier method is not considered acceptable due to the high failure rate when these barrier methods are combined.
 - [1c] periodic abstinence, declaration of abstinence just for the duration of a trial, and withdrawal are not acceptable methods of contraception.
 - [1d] male subjects with pregnant partners should use condoms during intercourse for the duration of the study and for at least 90 days after dosing.
 - [1e] male subjects should refrain from sperm and blood donation for the duration of the study and for at least 90 days after dosing.

- [1f] male subjects who are in exclusively same-sex relationships (as their preferred and usual lifestyle) are not required to use contraception.
- [2] are 30 to 55 years old, inclusive, at the time of screening.
- [3] have a body mass index (BMI) of 18.0 to 32.0 kg/m², inclusive, at screening.
- [4] have clinical laboratory test results within normal reference range for the population or investigative site, or results with acceptable deviations that are judged to be not clinically significant by the investigator.
- [5] have venous access sufficient to allow for blood sampling as per the protocol.
- [6] are willing to receive study treatment by SC injections.
- [7] are reliable and willing to make themselves available for the duration of the study and are willing to follow study procedures.
- [8] are able and willing to give signed informed consent.

6.2. Exclusion Criteria

Subjects will be excluded from study enrollment if they meet any of the following criteria at screening and/or check-in:

- [9] are investigative site personnel directly affiliated with this study and their immediate families. Immediate family is defined as a spouse, biological or legal guardian, child, or sibling.
- [10] are Lilly or Covance employees.
- [11] are currently enrolled in a clinical study involving an IP or any other type of medical research judged not to be scientifically or medically compatible with this study.
- [12] have participated, within the last 3 months, in a clinical study involving an IP. If the previous IP has a long half-life, 5 half-lives or 3 months (whichever is longer) should have passed, prior to dosing on Day 1.
- [13] have previously completed or withdrawn from this study or any other study investigating tirzepatide, and have previously received the IP.
- [14] have had any exposure to tirzepatide, other GLP-1 analogs, or other related compounds within the prior 3 months, or any history ever of allergies to these medications.
- [15] have any abnormality in the 12-lead ECG at screening that, in the opinion of the investigator, increases the risks associated with participating in the study.
- [16] have an abnormal blood pressure and/or pulse rate as determined by the investigator at screening or check-in.

- [17] have significant history of or current cardiovascular, respiratory, hepatic, renal, gastrointestinal, endocrine, hematological, or neurological disorders capable of significantly altering the absorption, metabolism, or elimination of drugs; of constituting a risk when taking the IP; or of interfering with the interpretation of data.
- [18] have evidence of significant active neuropsychiatric disease, as determined by the investigator.
- [19] have a positive alcohol breath test result or positive urine drug screen (confirmed by repeat) at screening or check-in.
- [20] show evidence of human immunodeficiency virus (HIV) infection and/or positive human HIV antibodies.
- [21] show evidence of hepatitis C and/or positive hepatitis C antibody.
- [22] show evidence of hepatitis B and/or positive hepatitis B surface antigen.
- [23] have used or plan to use over-the-counter or prescription medication, and/or herbal supplements (with the exception of vitamin/mineral supplements and/or thyroid replacement therapy) within 14 days prior to dosing and for the duration of the study, including any medications that reduce GI motility, including, but not limited to, anticholinergics, antispasmodics, 5-hydroxytryptamine-3 receptor antagonists, dopamine antagonists, and opiates.
- [24] have donated blood of more than 500 mL within the previous 3 months of study screening.
- [25] have an average weekly alcohol intake that exceeds 21 units per week, or are unwilling to stop alcohol consumption from 36 hours prior to check-in and while resident in the CRU (1 unit = 1/2 pint or 284 mL of beer; 25 mL of distilled spirits; 3 units = 250 mL of wine).
- [26] are unwilling to refrain from consuming caffeine- or xanthine-containing food and drink from 48 hours prior to admission and while resident in the CRU.
- [27] are currently or have been smokers, users of tobacco, users of nicotine replacement products, or users of any vaping/e-cigarette devices within the 3 months prior to admission and/or have positive cotinine at screening or check-in.
- [28] have had exposure to significant diagnostic, therapeutic, or employment-related radiation within 12 months prior to dosing (e.g., serial x-ray or computed tomography scans, barium meal, current employment in a job requiring radiation exposure monitoring).
- [29] have a history of constipation or have had acute constipation within 3 weeks prior to check-in.

- [30] have evidence of active renal disease (e.g., diabetic renal disease, polycystic kidney disease) or an estimated creatinine clearance of <80 mL/minute, calculated using the Chronic Kidney Disease-Epidemiology.
- [31] have participated in any clinical trial involving a radiolabeled IP within 12 months prior to check-in.
- [32] have a history or presence of pancreatitis (history of chronic pancreatitis or idiopathic acute pancreatitis), elevation in serum amylase or lipase (>1.5-fold the upper limit of normal [ULN]).
- [33] have a GI disorder (e.g., relevant esophageal reflux or gall bladder disease), or any GI disease which impacts gastric emptying (e.g., gastric bypass surgery, pyloric stenosis [with the exception of appendectomy]) or could be aggravated by GLP-analogs. Subjects with dyslipidemia and subjects who had cholecystolithiasis (with removal of gallstones) and/or cholecystectomy (removal of the gall bladder) in the past, with no further sequelae, may be included in the study, at the discretion of the investigator.
- [34] have a history of atopy or clinically significant multiple or severe drug allergies, or severe post-treatment hypersensitivity reactions (including, but not limited to, erythema multiforme major, linear immunoglobulin A dermatosis, toxic epidermal necrolysis, or exfoliative dermatitis).
- [35] have a personal or family history of medullary thyroid carcinoma or have multiple endocrine neoplasia syndrome type 2, or a screening calcitonin ≥ 20 pg/mL at screening.
- [36] have Gilbert's syndrome.
- [37] have serum aspartate aminotransferase (AST) or alanine aminotransferase (ALT) $> 2 \times$ ULN or total bilirubin (TBL) $> 1.5 \times$ ULN at screening.
- [38] have a history of malignancy within 5 years prior to screening.
- [39] have a triglyceride ≥ 5 mmol/L (442.5 mg/dL) at screening.
- [40] in the opinion of the investigator or sponsor, are unsuitable for inclusion in the study.

6.3. Lifestyle and/or Dietary Requirements

Throughout the study, subjects may undergo medical assessments and review of compliance with requirements before continuing in the study.

6.3.1. Meals and Dietary Restrictions

Subjects will be required to fast overnight for at least 8 hours before being administered the SC dose of tirzepatide, and when clinical laboratory test samples are taken (Schedule of Activities; Section 2). A meal will be offered to study subjects at approximately 2 hours postdose. During inpatient stays, subjects will receive a standardized, high-fiber diet at scheduled times that do not conflict with other study-related activities. Prune juice may be administered on an as-needed

basis to aid in normal bowel function and will not be considered a concomitant medication. Water may be consumed freely.

6.3.2. Caffeine, Alcohol, and Tobacco

- Caffeine - Subjects will refrain from consuming caffeine- or xanthine-containing food and drink from 36 hours prior to admission until discharge from the CRU.
- Alcohol - Subjects will not consume alcohol for 36 hours prior to admission until discharge from the CRU and will abide by study restrictions (i.e. no more than 3 units of alcohol per day - see Exclusion Criteria [25] for unit definition) at other times throughout the study.
- Tobacco - Subjects will not be permitted to smoke, use tobacco, or use products containing nicotine within 3 months prior to admission until final discharge from the study.

6.3.3. Activity

No strenuous physical activity will be allowed for 48 hours prior to dosing until discharge from the CRU, and 24 hours prior to each follow-up visit (inpatient and outpatient).

6.4. Screen Failures

Individuals who do not meet the criteria for participation in this study (screen failure) may not be re-screened.

7. Treatment

7.1. Treatment Administered

After an overnight fast of at least 8 hours, IP is to be administered subcutaneously to each subject by injection into the abdomen. The IP will consist of [¹⁴C]-tirzepatide to provide approximately 4.1 mg tirzepatide with approximately 100 µCi of radioactivity in each unit dose. The proposed [¹⁴C]-tirzepatide IP will be manufactured extemporaneously as sterile solutions for SC injection, as described in the Pharmacy Protocol approved by the sponsor. All doses will be administered by clinical site staff. The study regimen is indicated in [Table GPHX.2](#).

Prior to injection, the investigator or designee will clean the subject's skin and the injection will be administered to the lower abdominal quadrant, approximately 5 cm from the umbilicus (i.e., left or right lower quadrant). Detailed instructions for use will be provided by the sponsor. A limited number of clinical site staff will perform SC administration for consistency reasons.

Each dose syringe will be retained for analysis of residual radioactivity. Any unused assembled unit doses will be retained until completion of the study.

Table GPHX.2. Treatments Administered

Treatment Name	[¹⁴ C]-tirzepatide
Dosage Formulation	Solution
Unit Dose Strength/Dosage Level	Approx. 4.1 mg tirzepatide (~100 µCi)/1 mL
Route of Administration	SC injection
Delivery Method	Fixed Needle Syringe

Abbreviations: Approx. = approximately; SC = subcutaneous.

The investigator or designee is responsible for:

- explaining the correct use of the IP to the site personnel
- verifying that instructions are followed properly
- maintaining accurate records of IP dispensing and collection
- returning all unused medication to Lilly or its designee at the end of the study

